10.5 Trial Participation Card

Patients will be provided with a Trial Participation Card that provides the address and telephone number of the main contact for information on the study drugs and emergency contacts. The investigator and IRB will be instructed to keep this in their possession at all times.

10.6 Patient Confidentiality

Procedures for protecting patient privacy must adhere to applicable data privacy laws and regulations. In order to maintain patient privacy, all eCRFs, study drug accountability records, study reports, and communications will identify the patient by the patient number. The investigator will grant site monitors and auditors of the sponsor or a designee and regulatory authorities access to all source documents for verification of data collected on the eCRFs and for verification of the data collection process. The patient's confidentiality will be maintained and will not be made publicly available to the extent permitted by the applicable laws and regulations. The investigator and the sponsor are responsible for ensuring that sensitive information is handled in accordance with local requirements (eg, Health Information Portability and Accountability Act [HIPAA]). Appropriate consent and authorizations for use and disclosure and/or transfer (if applicable) of protected information must be obtained.

Data on patients collected on eCRFs during the study will be documented in an anonymous fashion, and the patient will only be identified by the patient number. In the

emergent or rare event that for safety or regulatory reasons it is necessary to identify a patient, the sponsor and the investigator are bound to keep this information confidential.

10.7 Study Monitoring

The sponsor or a designee will monitor the study to ensure that the study is conducted in accordance with ICH GCP requirements and the protocol. The study monitoring will be performed by a representative of the sponsor (site monitor) through on-site monitoring visits as frequently as necessary and frequent communications (e-mail, letter, telephone, and fax). The site monitor will review data recorded on the eCRFs, verify the eCRFs entries with direct access to source documents, collect any safety/efficacy information on patients, verify that amounts of unused study drug are accurate, and check retention of source documents.

10.8 Case Report Forms and Source Documents

10.8.1 Case Report Forms

The sponsor will supply eCRFs. The eCRF for each enrolled patient will be provided and historical information and study data, which are specified by the protocol, will be recorded on eCRFs by the investigator. All patient data from study visits must be collected on source documents and are promptly entered in the eCRFs in accordance with the specific instructions given. Electronic case report form entries will be performed by an investigator, subinvestigator, and study coordinator who are authorized in documentation. Data should be entered within 3 days after each patient's visit.

When queries are generated to the participating medical institutions for resolution by the sponsor or designee, eCRF data will be changed or a response will be recorded in accordance with the specific instructions given. The investigator must ensure that data reported on the eCRF is accurate, complete, legible, and timely and sign the eCRFs to verify the integrity of the data recorded.

A list of the reference ranges for all laboratory tests to be undertaken will be a part of the documentation to be collected prior to the initiation of study. The list of reference ranges for all laboratory tests should be updated if they are changed during the study. If a central laboratory has been selected to perform any or all tests, it is essential that all the reference ranges for the laboratory tests to be analyzed at the laboratory should also be collected.

10.8.2 Source Data and Source Documents

Source documentation supporting the eCRF data should indicate the patient's participation in the study and should document the dates and details of study procedures, AEs, and patient status. However, the following data can be directly recorded on an eCRF as source data:

- Reason for use of prior therapy or concomitant therapy
- Severity, seriousness, causal relationship to the study drug of AE
- Any comments inserted into eCRF

Listed below are data captured only in the eCRF (ie, items automatically-calculated by the electronic data capture system):

- Age
- BMI
- Respiratory rate (breaths/minute)

The investigator must maintain source documents, such as laboratory reports, and complete medical history and physical examination reports. All the source documents must be accessible for verification by the site monitor(s), auditor(s), the IRB/IEC, and inspections of regulatory authority. Direct access to these documents must be guaranteed by the investigator, subinvestigator, or study coordinator, who must provide support at all times for these activities. For all sources of original data required to complete the eCRF, the nature and location of the source documents will be identified by the sponsor and the site staff. If electronic records are maintained at the medical institution, the method of verification must be specified in document within the medical institution.

10.8.3 External Data

The following data will be reported in separate documents from the eCRFs.

- Plasma concentrations of S-033447 (determined according to procedures specified in a separate document)
- Results of virology test (determined according to procedures specified in a separate document)
- Safety laboratory tests

10.9 Committees

10.9.1 Independent Data Safety Monitoring Board

An independent DSMB will be established for this study. Details of the DSMB composition, roles and responsibilities, and processes will be documented in a separate DSMB charter.

10.10 Termination or Suspension of the Study

10.10.1 Termination or Suspension of the Entire Study

The sponsor may prematurely terminate or suspend the study at any time for the following reasons:

- Ensuring safety of the study is difficult due to safety concerns (eg, occurrence of serious, treatment-related AEs)
- Achieving the purpose of the study is considered impossible (eg, interim data suggesting lack of safety, inadequate recruitment of patients)

If the study is prematurely terminated or suspended, the sponsor will promptly inform the investigators. The investigator or subinvestigator should promptly inform the participating patients and change the study treatment to other appropriate therapy.

For withdrawal criteria for individual patients, see Section 7.8.

10.10.2 Termination or Suspension of the Study by Medical Institution

The investigator may prematurely terminate or suspend the study in the study center with agreement of the sponsor at any time when the investigator considers that ensuring safety of the study is difficult due to safety concerns (eg, occurrence of SAEs).

The sponsor may request the investigator to prematurely terminate or suspend the study in the study center at any time when major deviations to the protocol, other procedures, and ICH GCP guidelines are not corrected.

If the study is prematurely terminated or suspended, the investigator or subinvestigator should promptly inform the corresponding IRB/IEC and participating patient and change the study treatment to other appropriate therapy.

10.11 Protocol Modifications and Deviations

The investigator will conduct the study in compliance with the protocol provided by the sponsor and approved by the IRB and the regulatory authorities. Modifications to the protocol should not be performed without agreement of both the investigator and the sponsor. Changes to the protocol will require written IRB approval prior to implementation, except when the modification is needed to eliminate an immediate hazard(s) to the patients.

The investigator or subinvestigator should document any deviation from the protocol and the reason. If the investigator deviates from the protocol or makes a change to the protocol to eliminate an immediate hazard(s) to the patients, the record should be immediately submitted to the sponsor, the study center, and the IRB by the investigator and the IRB will provide expedited review and approval. After obtaining approval from the IRB, the investigator must obtain a written agreement of the sponsor through the study center.

When deviation from the protocol is required to eliminate immediate hazard(s) to the patients, the investigator will contact the sponsor, if circumstances permit, to discuss the planned course of action. Any deviations from the protocol must be fully documented in the source document.

10.12 Data Management

The sponsor or a designee will be responsible for data management and analysis. These procedures are specified in a separate document.

10.13 Retention of Data

The study documents must be maintained as specified in the ICH GCP and as required by the applicable regulatory requirements. The investigator and study center should take measures to prevent accidental or premature destruction of these documents.

If the sponsor is granted manufacturing and marketing approval for the drug, the sponsor will promptly notify the head of the study center in writing.

Records will be retained for the longer of either 1 of the following periods:

- Until the approval day of manufacturing/marketing on the study drug or 3 years after the decision day on the discontinuation of development
- 3 years after the decision day on the discontinuation or completion of the study

However, the duration of retention may be prolonged with agreement with the sponsor. If the investigator withdraws from the responsibility of keeping the study records, custody must be transferred to a person willing to accept the responsibility.

10.14 Quality Control and Assurance

The sponsor or a designee will implement and maintain quality control and quality assurance procedures with written standard operating procedures to ensure that the study is conducted and data are generated, documented, and reported in compliance with the protocol, ICH GCP, and applicable regulatory requirements.

This study will be conducted in accordance with the provisions of the Declaration of Helsinki and all revisions thereof; in accordance with the ICH GCP and as required by the applicable regulatory requirements.

The sponsor will provide training necessary for the study to the investigators and the study center personnel prior to the initiation of the study.

10.15 Publication and Disclosure Policy

All information regarding S-033188 supplied by the sponsor to the investigator is privileged and confidential. The investigator agrees to use this information to accomplish the study and will not use it for other purposes without consent from the sponsor. It is understood that there is an obligation to provide the sponsor with complete data obtained during the study. The information obtained from the clinical trial will be used toward the development of S-033188 and may be disclosed to regulatory authorities, other investigators, corporate partners, or consultants as required.

The sponsor will retain ownership of all data. All proposed publications based on the study will be subject to the sponsor's approval requirements.

10.16 Financial Disclosure

The information on financial disclosure for investigators will be addressed in a separate agreement between the sponsor and the investigator.

Appendix 1 Time and Events Schedule

			Treatment Period					Follow-up Period									
		D1	D2	D3	D4	D5	D6	D7	D8	D9	D10	D11	D12	D13	D14	D15	D22/ ET
		V1	V2	V3	OpV1	V4	OpV2			V5						V6	V7
	ndow (days)	-	-	+ 1	-	+ 1	-			± 2						± 3	± 3
	Consent/Assent	Х															
	/Exclusion Criteria	Х															
Demogra		Х															
Medical I		Х															
-	luenza Diagnostic Test	Xp															
Randomi		Х															
	ug Dispensation	Х															
Study Dr	ug Administration	Х	Х	Х	Х	Х											
	Body Temperature Measurement	$\mathbf{X}^{\mathbf{d}}$	4 Tim	es Daily					Twi	ce Daily	7						
Patient	Assessment of Severity of Influenza Symptoms	$\mathbf{X}^{\mathbf{d}}$				Twice I	Daily					C	Once Dai	ily			
eDiary ^c	CPI	X ^d		Twice Daily Once Daily													
	Assessment of Health	X ^d		Once Daily													
	Assessment of Health Prior to Influenza Symptoms	$\mathbf{X}^{\mathbf{d}}$															
WP Ques			X (following resolution of symptoms)														
Assessme Complica	Assessment of Influenza-related Complications (sinusitis, bronchitis, otitis media, pneumonia)		x	х	x	х	x			x						x	х
	ical Examination	X ^{e, f}															Xe
Symptom Examinat	n-focused Physical tion		х	х	x	х	х			X						х	
Concomi	tant Therapies		Х	Х	X	Х	Х			X						X	Х
	ug Accountability		Х	Х	X	Х	Х			1							
	egnancy Test (WOCBP) ^g	Х				Х											Х
	Immunological Tests																
Routine Laboratory Tests (hematology and blood chemistry)		х				х										x	х
	Influenza Antibody Titer Test																X
Nasophar (if nasopl	ryngeal (preferred)/pharyngeal haryngeal cannot be collected) 7irology Test)	X ^h X ^h	х	х	x	х	х			x						X ⁱ	X ^{i, j}

Vital Sign Measurements	Х	Х	Х	Х	Х	Х		Х			Х	Х
Electrocardiography	Х	Х										Х
Pharmacokinetic Blood Samples	Xk	Х	Xk		X						Xk	
Adverse Event Assessments	Х	Х	Х	Х	X	Х		Х			Х	Х
Record if Meal Eaten and Time	Х											
Intrahousehold Infection Interview (for	v	v	v		v			v			v	
Japan only)	л	л	л		л			л			л	

D = day; eDiary = electronic diary; CPI

; ET = early termination; OpV= optional visit; V = visit; WOCBP = women of childbearing potential;

WP = work productivity

a Include a review of prior therapies.

b Not necessary if a site has performed a RIDT prior to consideration for the study.

c The patient will measure or assess and record in the patient diary, body temperature 4 times daily (morning, noon, evening, and bedtime) from Days 1 to 3 and twice daily (morning and evening) from Days 4 to 14; assessment of health once daily (evening) from Days 1 to 14; the severity of influenza symptoms twice daily (morning and evening) from Days 1 to 9 and once daily (evening) from Days 10 to 14; and the CPI twice daily (morning and evening) from Days 1 to 9 and once daily (evening) from Days 2 or ET.

d Predose; if the study treatment is initiated at 18:00 or later on Day 1, the patient will not need to perform the Day 1 evening assessments.

e Including measurement of body weight.

f Height and body mass index will be measured at the predose examinations only.

g Urine pregnancy test will be performed only for females who are not diagnosed as postmenopausal.

h Predose.

i To be collected if the investigator determines that flu symptoms are persisting.

j If the investigator determines that flu symptoms are persisting at ET.

k Blood samples will be collected for the measurement of plasma drug concentrations once each at Visits 2 (Day 2) and 4 (Day 5). If circumstances permit, samples also will be collected within the period from 0.5 to 4 hours after the initial dose at Visit 1 (Day 1), at Visit 3 (Day 3), and at Visit 6 (Day 15).

Quality-of-Life Questionnaire Appendix 2

CPI

Study center name	
Patient identification code	
Visit	
Date	

Under each heading, please tick the ONE box that best describes your health TODAY.

CPI

CPI

Appendix 3 Work Productivity Questionnaire

Work Productivity Questionnaire Cover Note

To the investigator:

This questionnaire is designed to capture the impact of influenza symptoms on patients' ability to work and perform normal activities. We would like the patient to complete the questionnaire once, during the earliest clinic visit following resolution of symptoms.

[figure not shown]
- 1. How many hours or days per week do you work (eg, full or part time paid work, voluntary work, or study)?
- 2. Due to your recent influenza illness, for how many hours or days were you unable to work? __hours, or ___ days
- 3. Due to your recent influenza illness, for how many hours or days did you feel that your symptoms caused you to perform below your normal standard even though you attended work? ____hours, or _____days
- 4. Due to your recent influenza illness, for how many hours or days did you require someone to help you with your normal activities? ____ hours, or ____ days

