2.6 Health Economic Outcomes Research Objectives

 To compare the total quality-of-life detriment by measuring the CPI and a work productivity (WP) questionnaire, in patients treated with of S-033188 compared with oseltamivir 75 mg BID for 5 days and placebo

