7.7.4 Health Economic Outcomes

7.7.5 Work Productivity Questionnaire

The WP questionnaire will be completed at Day 22, or at the earliest clinic visit following alleviation of symptoms. These assessments are included in Appendix 3. The work productivity questionnaire consists of 4 questions regarding employment, number hours worked, productivity while at work, and requirement for personal assistance.

The work productivity questionnaire will be completed on paper.

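### The work productivity form takes answers in hours or days without a visible question on hours per working day, so part of the work-loss data can be put in one unit only by an assumed conversion

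*Protocol*

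**What the plan says.** Protocol Section 2.6 makes the questionnaire part of a stated three-arm comparison: "To compare the total quality-of-life detriment by measuring the CPI and a work productivity (WP) questionnaire". The synopsis lists it under the other endpoints, within health economic outcomes.

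The form is printed in Appendix 3. Question 1, on usual work, reads "How many hours or days per week do you work (eg, full or part time paid work, voluntary work, or study". Question 2, on work missed, asks "for how many hours or days were you unable to work". Question 3, on reduced performance, asks "for how many hours or days did you feel that your symptoms caused you to perform below your normal standard even though you attended work". Question 4 asks "for how many hours or days did you require someone to help you with your normal activities". Questions 2 to 4 print one blank for hours and another for days as alternatives. No conversion is stated.

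Section 7.7.5 describes the form as "4 questions regarding employment, number hours worked, productivity while at work, and requirement for personal assistance" and adds: "The work productivity questionnaire will be completed on paper". The cover note in Appendix 3 has each patient fill it in once, at the first clinic visit after symptoms have resolved. Section 9.13.4.2 leaves the analysis variables and methods to the SAP, which is not at hand.

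**The concern.** Work loss can be expressed as hours or as a share of the usual working week. Hours need either an answer in hours or the length of that patient's working day. A share needs question 1 and the loss question in the same unit, or again the length of the day. The visible form leaves the unit to the patient each time and does not ask for the length of the day. It also names part-time work, voluntary work and study in question 1, so day lengths can be expected to differ widely.

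Choosing the analysis variable and any conversion belongs to the SAP, and the absence of a conversion rule from the protocol is no defect. The point concerns the input. A SAP written later cannot add an item to a paper form that each patient completes once. At stake is the precision and interpretability of the work-loss comparison between S-033188, oseltamivir and placebo.

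**Working it through.** The plan gives no figure on this point to reproduce. The check is unit arithmetic.

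**Inputs.** From Appendix 3: hours or days in all four questions, and no visible hours-per-day item. Assumed, because the protocol gives no values: a working day of 4 to 12 h, a working week of 3 to 7 days, and the example answers below.

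**1. Matching units.** Share of usual week lost = question 2 / question 1. In days, 3/5 = 0.60. In hours, 24/40 = 0.60. The length of the day cancels, so these forms give an exact share. The same holds for question 3.

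**2. Hours lost from an answer in days.** Hours = days × hours per day. The error of a fixed 8 h rule is (8 − h)/h. For 3 days lost:

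| Assumed h per day | Hours lost | 8 h rule gives | Error |
|---|---|---|---|
| 4 | 12 | 24 | +100% |
| 6 | 18 | 24 | +33% |
| 8 | 24 | 24 | 0% |
| 10 | 30 | 24 | −20% |
| 12 | 36 | 24 | −33% |

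**3. Question 1 in hours, question 2 in days.** Take 40 h per week and 3 days lost, with d working days per week. Share = 3/d and hours lost = 3 × 40/d.

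| Assumed days per week | Share | Hours lost |
|---|---|---|
| 3 | 1.00 | 40.0 |
| 4 | 0.75 | 30.0 |
| 5 | 0.60 | 24.0 |
| 6 | 0.50 | 20.0 |
| 7 | 0.43 | 17.1 |

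For a 20 h/week worker, the 8 h rule gives 3 × 8 = 24 h lost, or 24/20 = 120% of the usual week. If that patient works five days of 4 h, the true loss is 3 × 4 = 12 h, or 12/20 = 60%.

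**4. Question 1 in days, question 2 in hours.** Take 5 days per week and 24 h lost. Share = 24/(5 × h), which is 1.20, 0.80, 0.60, 0.48 or 0.40 at 4, 6, 8, 10 or 12 h per day.

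**5. Question 4.** Help with normal activities is not tied to a working day, so question 1 cannot convert it. If a day of help means 8 to 24 h (assumed), the factor is 24/8 = 3.

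**6. After the fix.** With 8 h per day on 5 days per week, 3 days lost is 24 h, or 24/40 = 60% of the week. With 4 h per day on 5 days, it is 12 h, or 12/20 = 60%. Each form then has a single value.

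**The case against.** The strongest objection is that this can be handled in the analysis. A reader might infer from the form that work loss cannot be put on one scale and that no SAP rule could help. The documents do not support that. Matching units give an exact share without any day length, and for the remaining forms a SAP can declare a conversion with a sensitivity range. What stands against the objection is narrower: for those forms the common scale rests on an assumption that one more blank would have made unnecessary.

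Second, the text available omits a figure just before question 1 and shows no answer field for that question, so a wording there that settles the unit cannot be excluded. Section 7.7.5 counts four questions, which speaks against a separate fifth item. It does not rule out a two-part answer to question 1. If that field already asks for both hours and days per week, the day length follows by division and the point falls for questions 2 and 3.

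Third, the frequency is unknown. A reader might assume that unit choices are independent and that a large fraction of forms would be mixed. Nothing in the protocol supports this. Patients answering on one page may well keep to one unit, and then no form mixes units, although answers in days would still need a conversion to give hours.

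Fourth, a reader might see a contradiction in Section 7.7.5, because it speaks of hours worked. That phrase is a topic label in a one-sentence summary and does not specify a unit.

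Fifth, a reader might add that questions 2 to 4 cover the whole illness, including time before the first dose, and that this dilutes the treatment effect. Whole-illness burden is a coherent quantity and fits the objective of total detriment. Loss before dosing is balanced in expectation by randomisation and does not bias the absolute difference. The 114 h and 150 h in Section 9.2 cannot size any dilution, because they are assumed times to symptom improvement and not work loss.

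**Conclusion.** The point holds as a minor measurement defect. On the visible form, hours lost for any answer in days, and shares for any form that mixes units, depend on an assumed conversion. Over an assumed 4 to 12 h per day, 3 days lost means 12 to 36 h, and a fixed 8 h rule errs by −33% to +100%. The share of the usual week remains exact wherever units match.

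The unit choice is open in the same way to all arms of a blinded trial, so the expected effect is mainly noise. A wrong fixed factor would also rescale a between-arm difference in hours: a difference of 1 day becomes 8 h under the 8 h rule, against 4 to 12 h over the assumed range.

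The conclusion assumes that question 1's unseen answer field does not already collect both hours and days. The primary endpoint, the sample size and the control of type I error are not affected.

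**What to change.** In question 1, ask for both the usual hours per day and the usual days per week, each with its own blank. Questions 2 and 3 can then stay in either unit and be converted patient by patient. Give question 4 a single fixed unit, since no working day applies to it. For patients with irregular hours, the hours-per-day answer will be an average, which is still closer than one factor for everyone.

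The cost is a revised one-page paper form, its translations, and one more blank for the patient. No visit or assessment is added. The change has to come before the form is in use. For forms already completed, the SAP can analyse the share of the usual week where units match, and apply a declared conversion with a sensitivity range elsewhere.
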